### 3.6 Measure the impact of CDI management on the healthcare system and the impact of current control measures (infection control/antibiotic stewardship). (Objective 2.6)

#### 3.6.1 Study rationale

Although it appears self-evident that CDI can be prevented by infection control and antimicrobial stewardship, this has only been demonstrated in the setting of outbreaks by selected strains and only for complex intervention bundles. It is currently unknown which measures are best at preventing CDI and which are most cost-effective. For CDI treatment, calculations have been modelled , but for preventive measures such data need to be generated. Using data from Objectives 1.5, 2.1, 2.2 & 2.4, we will determine the diagnosis and treatment costs for those cases managed vs. not managed according to current guidelines. Results of cost-effective measures will be presented/visualized by using threshold analyses. Potential cost-savings are likely by e.g. shortened overall length of stay, prevention of severe and multiple CDI, transfer to (expensive) intensive care unit (ICU), and morbidity/mortality due CDI. Calculation of overall costs (direct and indirect costs) will be based on methodology as stated in O2.5.

#### 3.6.2 Outcome measures

This section of COMBACTE-CDI is surveillance of existing guidelines, including local knowledge and compliance. There is no fixed outcome measure for this.

#### **3.6.3** Sampling Criteria for surveillance studies (objective 2.6)

#### 3.6.3.1 Inclusion criteria

All data generated from samples and isolates collected on the sample days (O1.1 and 1.2), all participants from the case/controls studies (O1.3 and 1.4), all participating sites (hospital based), and their associated community healthcare providers who submitted samples on the sampling days (sample source sites). In four selected countries an additional 10 nursing homes that did not submit samples on the sampling days will also be asked to complete the surveillance questionnaire, as there are a paucity of CDI data regarding these facilities.

#### 3.6.3.2 Exclusion criteria

None

#### 3.6.4 Study methods

The investigators will a execute cost-benefit analyses of the different CDI management policies/pathways highlighted from Objectives 2.1, 2.2, 2.3 and 2.4, and identify the most cost-effective. The most cost-effective policy is expected to differ between healthcare settings as identified in 2.5. Cross-country comparisons of prices for health services will be based on OECD data. Data from Objective 1.2 will enable us to calculate differential costs per *C. difficile* strain/ribotype, and to what extent cost-effectiveness of infection control/antimicrobial stewardship (AMS) measures is driven by local CDI epidemiology. So-called hypervirulent strains 027/078/244 may be pooled for such analysis. It is well known that CDI due to hypervirulent strains leads to high rates of morbidity and mortality. Excessive direct costs may be expected, especially if patients are treated on an Intensive Care Unit e.g. due to toxic megacolon or pseudomembranous colitis). Further indirect costs may arise in case of productivity losses as stated in 02.5.

The investigators will calculate the value of infection-control measures including the identification of high-risk patients and, using data from Objective.1.5, we will analyse the economic value of preventing transmission. Using data from Objective 2.5, we will determine the potential reduction in CDI economic burden in individual healthcare settings by introducing or changing infection control/AMS measures. Therefore, expenditures for direct cost factors (e.g. personnel costs for Infectious Diseases specialists) will be compared with in- and outpatient cost-savings (e.g. due to prevention of CDI). Based on these results we will calculate the optimal approach, taking into account an institution's economic burden. This could be helpful to implement standardised and effective infection control/AMS measures into clinical practice to improve patient outcomes and reduce overall costs associated with CDI across Europe in all healthcare settings. Furthermore, these results could be of interest for consideration of updated guidelines. Calculation of costs will be based on methodology as stated in O2.5.

#### 3.6.5 Sample size

As this analysis requires data from the objectives O1.1-15 and O2.1-2.5, the sample size is dependent on the sample size of these previous objectives. It will include;

- The number of samples collected on the sampling days (O1.1) and
- The number of isolates of *C. difficile* (01.2),
- The number of participants in the case/control studies (O1.3 and 1.4),
- The data generated in the transmission modelling (01.5),
- The number of completed surveillance questionnaires (O2.1-2.5) as described above.

#### 3.6.6 Data collection

The anonymised datasets generated from work-package 1 (O1.1-1.5) will be combined by the University of Leeds (overall guardian of the data) and sent to University of Cologne (a COMBACTE-CDI partner) for analysis as part of the cost-benefit modelling. This dataset will contain anonymised health information; it will not contain any personal identifiable data. This will be combined with the surveillance data (O2.1-2.5).

As described above, for the surveillance data, an online data capture system will be used to collect the data, built within the COMBACTE online network. This data will not contain any personal data, but details about individual sites knowledge and compliance with existing guidelines. Each sample source site will have a unique anonymised study identifier for the online data capture system; investigators will therefore not be able to identify the sample source sites.

The main dataset will then be accessed via the online portal by the investigator for this objective. Rule bases will be added to ensure that each objective investigator can only access data relevant to their objective.

#### 3.6.7 Data Analysis

A simulation of the economic impact of novel CDI treatment options will be made using data from Objectives 1.4 & 1.5.

For the simulation of costs, a decision-analytic model (e.g. decision tree analysis, markov model) will be appropriate. Therefore, a separate analysis of direct/indirect costs factors as well as further methodology as stated above will be performed/used to determine the impact of treatment interventions as well as changes in diagnostic pathways.

Building on data collected in WP1 (esp. the modelling in 1.5) and in O2.5, resource-utilization analyses will be performed for different CDI management approaches according to healthcare setting.

Data from O1.2 will be used to calculate differential costs per *C. difficile* strain/ribotype, and to what extent cost-effectiveness of infection control/antimicrobial stewardship (AMS) measures are driven by local CDI epidemiology.

The value of infection-control measures including the identification of high-risk patients will be calculated, and, using data from O1.5, the economic value of preventing transmission will be assessed.

### 4.0 Data management

All data generated during work package 1 will be under the guardianship of the University of Leeds. It will be held on secure, password protected encrypted University servers. No personal identifiable data will be held, only health data against a pseudoanonymised study number. The link back to the participant will only be held by the clinical care team, this link back will never be disclosed to the investigators or leave the clinical participating site. The link back (retained at the clinical site) is essential however to enable the clinical care team to fill in the follow up CRFs for the case/control study. Once the CRF data has been collected and validated and verified the link-back will be destroyed by the local study site.

This anonymised dataset will also be transferred to a sub-contractor (still to be defined) for the transmission modelling. The sub-contractor will be within the EEA, and will be subject to a full

document review by the University of Leeds, to ensure they comply with all of the relevant regulatory requirements. Their responsibilities will be clearly defined within the sub-contract and data transfer agreement between the University of Leeds and the sub-contractor. Once finalised, the data required for, and generated by the transmission modelling will transfer back to the University of Leeds for storage on secure, password protected encrypted University servers. No data will be held locally by the sub-contractor after completion of the modelling.

In work package 2, an online data capture system will be used to collect the surveillance data, built within the COMBACTE online network. The data will be held on secure, password protected servers at the University of Utrecht (a COMBACTE-CDI partner). This data will not contain any personal data, but details about individual sites knowledge and compliance with existing guidelines. Each sample source site will have a unique anonymised study identifier for the online data capture system; investigators will therefore not be able to identify sample source sites. The main dataset will then be accessed via the online portal by the investigators for each of the objectives. Rule bases will be added to ensure that each objective investigator can only access data relevant to their objective.

The anonymised datasets generated from work package 1 (O1.1-1.5) will be combined by the University of Leeds (overall guardian of the data) and sent to University of Cologne for analysis as part of the cost-benefit modelling. This dataset will contain anonymised health information; it will not contain any personal identifiable data. This will be combined with the surveillance data (O2.1-2.5). These data will be held on the secure, password protected servers at the University of Cologne (a partner within COMBACTE-CDI). Data transfer agreements are in place between the University of Leeds and the University of Cologne, as part of the consortium agreement. As the University of Cologne is a partner within COMBACTE-CDI, this data will be archived locally, not transferred back to University of Leeds.

### **5.0 Reporting**

This is strictly an observational (surveillance) study. Results of additional testing will not be reported back to participating laboratories. The study is therefore 'non-interventional' as the participant samples will be processed as per local policy at each hospital and those results acted upon; i.e. additional COMBACTE-CDI study results will NOT be available for patient management.

Study reports and conclusions based on analysis of data at a national and European level will be prepared by the lead investigator for each objective.

A full study report will be presented at the end of each objective. Results will be submitted for presentations at scientific meetings followed by preparation of manuscript and publication whenever applicable. Authorship will be led by the lead investigator for each objective (see consortium agreement).

# **Appendix 1**

Country	Recruitment of study sites which test both in- patient and community (GP, long term healthcare facilities) stool samples	Collection of residual diagnostic tissue and export to the UK	Collection of prospective patient data (outcome data)	Collection of retrospective patient data (risk factor data)	Collection of attributable costs of CDI data	Collection of data regarding testing policy and methodology, surveillance practices, national guidelines and compliance and patient testing and treatment stratification (severity markers)	Region of Europe a	Population (average from two sources b )	Study sites 1 per 3m population
Slovakia	Yes	Yes	Yes	Yes	Yes	Yes	Eastern	5463801	2
Poland	Yes	Yes	Yes	Yes	Yes	Yes	Eastern	38421407	13
Romania	Yes	Yes	Yes	Yes	Yes	Yes	Eastern	20486235	7
UK	Yes	Yes	Yes	Yes	Yes	Yes	Northern	64770786	22
Ireland	Yes	Yes	Yes	Yes	Yes	Yes	Northern	4833233	2
Sweden	Yes	Yes	Yes	Yes	Yes	Yes	Northern	9511327	3
Spain	Yes	Yes	Yes	Yes	Yes	Yes	Southern	47314040	16
Italy	Yes	Yes	Yes	Yes	Yes	Yes	Southern	60904272	20
Greece	Yes	Yes	Yes	Maybe	Yes	Yes	Southern	10846356	4
France	Yes	Yes	Yes	Yes	Yes	Yes	Western	65617845	22
Netherlands	Yes	Yes	Yes	Yes	Yes	Yes	Western	16998349	6
Austria	Yes	Yes	Yes	Yes	Yes	Yes	Western	8397080	3

Table 1. Results of an initial feasibility assessment for conducting the study in O1.1 in Europe.a = UN geocheme for Europe, zones of Europe; b = bwww.geoba.se, and www.worldmeters.info.

# **Appendix 2 Participating site invitation letter**

Dear Sir/Madam,

We are writing to invite you to be a participating site in the Combatting Bacterial Resistance in Europe – *Clostridium difficile* Infections (COMBACTE-CDI) project which aims to develop a detailed understanding of the epidemiology and clinical impact of CDI across Europe.

This research project received support from the Innovative Medicines Initiative Joint Undertaking under grant agreement, resources of which are composed of financial contribution from the European Union Seventh Framework Programme (FP7/2007-2013) and EFPIA companies in kind contributions.

We are the national coordinating laboratory for XXXXXXX and are recruiting sites to take part in this study.

All sites **must** meet the following criteria:

- Sites must carry out diagnostic testing of faecal samples from both in-patients **and** community patients
- Sites must be able to collect residual diagnostic tissue of all faecal samples received by the laboratory on a specified date in May/June and October 2018, and export this to the UK the day after collection (transport provided)
- Sites must be able to collect prospective patient data (outcome data) linked to the faecal samples provided during the sampling period (based on a provided Case Report Form) either directly or via the **sample source site**
- Sites must be able to collect retrospective patient data (risk factor data) linked to the faecal samples providing during the sampling period (based on a provided Case Report Form) either directly or via the **sample source site**
- Sites must be able to provide data in regards to their CDI testing policy and methodology, CDI surveillance practices, knowledge of national CDI guidelines and their local compliance, and CDI treatment (including according to patient level risk e.g. CDI severity) (based on a provided questionnaire).

If you agree to take part, you would be required to collect all unformed faecal samples (after the completion of all routine microbiology tests) received on two selected sampling days in the year (May/June and October) and send them to the European Coordinating Laboratory in Leeds, UK. A one-off fee of €500 Euros is payable to yourselves, to cover the labour and consumables costs incurred in sending the samples to Leeds. You will receive shipping packaging and shipping instructions to ship the samples to Leeds using DHL. The cost of shipping is covered by the European Coordinating Laboratory.

The European Coordinating Laboratory will test each sample included in the study for CDI using the recommended 'optimal' testing methodology (ESCMID guidelines). Results will be compared to those obtained from your submitting hospital/laboratory, including if the sample was even tested.

All *C. difficile* isolates collected from the study samples will then be typed by various methods including PCR-ribotyping, toxinotyping and whole genome sequencing.

All CDI positive cases (as determined by the European Coordinating Laboratory), and a proportion of negative cases (at the ratio of 1 case to 3 controls) will have clinical data collected (6 months after each sampling date) on patient outcomes and risk factors for disease Data will be collected on a Case Report Form and sent to the European Coordinating Laboratory for analysis. A fee of €200 Euros is payable to yourselves, to cover the labour costs incurred in completion of each CRF.

Each participating site (and their associated community practices) will also be asked to complete a web-based questionnaire on guideline knowledge, compliance, testing policy and methodology, surveillance practices, and stratification of 'severe' patients. Data will be compared to identify differences between countries and healthcare providers. A one-off fee of €100 Euros is payable to yourselves to cover the labour costs incurred in completion of the questionnaire and a further one-off fee of €100 Euros is payable to yourselves to cover the administration in distributing the questionnaire to your associated community practices.

If you wish to participate in this study please confirm your participation via email to XXXXXXXX by the 16th February 2018. You will then be provided with a study pack for the initial sampling and copy of the full study protocol and study manual. You will also receive an email from our COMBACTE partner, LAB-NET [contact] requesting you to complete a questionnaire so that you can be added to the COMBACTE LAB-NET system. We ask that you complete this at your earliest opportunity.

We hope that you understand the value of this project and agree to participate in this study.

Yours sincerely

Name

National Coordinator of Country for COMBACTE-CDI

Contact details

This Research project receives support from the innovative Medicines initiative Joint Undertaking under grant agreement nº 115523 | 115620 | 115737 | 777362 resources of which are composed of financial contribution from the European Union Seventh Framework Programme (FP7/2007-2013) and EFPIA companies in kind contribution.

Appendix 1. Variable description table

## 1. Introduction

This statistical analysis plan (SAP) is to provide a description of the study design, study variables, and statistical analysis methods for the COMBACTE-CDI study, which aims to develop a detailed understanding of the epidemiology and clinical impact of CDI. More specifically, this project's objectives are to:

- Align and understand the unmet public health needs relating to CDI;
- Identify and quantify the direct and long-term burden of CDI on healthcare systems

The COMBACTE CDI case/control studyfollows a cohort of patients identified during the COMBACTE CDI sample collection study. The sample collection study involved 119 sites from 12 countries from Europe, with a national coordinator recruited for every country. National coordinators selected participating sites (PS) to cover all major geographical regions within every country. Participating sites were recruited at a rate of one per 3 million population in all study countries. Figure 1 shows the full study design.

Figure 1. Schematic representation of study design (WP1 &WP2). A synergistic approach will enable completion of all the objectives from WP1 and WP2, with data created from a single, large complex study flowing into other objectives for further results analysis. Boxes in blue denote objectives in WP1, and those in orange denote for objectives in WP2. Due to the inter-related nature of the

objectives within both WP1 and WP2, the flow of work has been planned to ensure maximum outputs within the timeframe of the grant. The directions of the arrows indicates data flow and, therefore, also the timing of activities; i.e. Strains cannot be analysed (1.2) until after they have been collected (1.1). This ambitious comprehensive project design takes influence from several existing, separate studies; the scope of producing all of these is data from one, well-designed and far-reaching study is novel and innovative.

During the COMBACTE-CDI sample collection study, cases and controls were identified; Multiple diagnostic definitions of a case;

- Case defined as C. difficile toxin positive (gold standard method CCNA) positive
- Case defined as C. difficile toxin positive (new novel method –SIMOA)
- Case defined as free toxin negative but positive for a cytotoxigenic strain (by culture or detection of toxin gene)
- Control defined as negative by all assays

This enriched case/control study will provide data on the difference in severity of CDI and the risks and outcomes for these different 'diagnostic types'. There are a paucity of data on these differences, particularly with regard to the new technology of the SIMOA assay. A retrospective CDI case-control study is proposed to determine the outcomes and risk factors for CDI, but different diagnostic criteria, for patients both within the hospital setting and in the community.

Ethical and regulatory approvals are in place for each site within the case/control study, as per the COMBACTE-CDI full study protocol.

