## 2.1 Selection of case and controls (total possible to be recruited)

		Location	of participant a sample	at time of
Diagnostic categories:		Hospital	Community	TOTAL
CDI positive cases	1. CCNA positive	83	20	103
	2. CCNA negative/Simoa positive	49	22	71
	3. CCNA and Simoa negative but CTC positive or bioFire pos	24	15	39
CDI negative controls	4. Negative control *	365	147	512
Total number selected for case/control study 521 204		725		

Table1. The total number of samples selected for the case/control study (n=725). The table shows the number of CDI positive cases according to the indicated diagnostic categories (1-3, n=213) and by location of participant (Hospital n=156, Community n=57). Negative controls (4, n=512) were selected at a rate of 1:3 from matching participating sites (one case to three controls). As some participating sites had less than 3 controls per case, average rate was of 1:2.4 (one case to 2.4 controls) (\*).

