#### 2.5. Analysis objectives

The main objectives of the analyses are to;

- 1. Determine the outcomes of cases (of each classification) vs controls, and compare between countries and hospital vs community cases
- 2. Determine the risk factors for cases (of each classification) vs controls, and compare between countries and hospital vs community cases

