#### 4.1 Inclusion-exclusion criteria

#### 4.1.1 Inclusion criteria

- 1. A case is defined as a patient who;
  - a. had a *C. difficile* toxin positive (gold standard method CCNA) stool sample
  - b. had a *C. difficile* toxin positive (new novel method –SIMOA) stool sample
  - c. had a free toxin negative stool sample but was positive for a cytotoxigenic strain (by culture or detection of toxin gene)
- 2. A Control is defined as a patient who had a sample included int eh sample collection study but tested negative by all assays

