#### 4.2 Analysis sets and subgroups

Data will be analysed to determine the outcomes and possible risk factors for CDI based on the different diagnostic criteria. Comparisons will be made between outcomes and risks for different countries and healthcare settings (hospital, community). Sample size will be too small to perform subgroup analysis within each country.

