## 7. Statistical methodology and statistical analysis

#### 7.1 Descriptive analysis

Distribution of demographic, concomitant pathogens, medical conditions, medical procedures, and medication used will be tabulated by case and controls. The analysis will also be stratified by age group (<18, 18-49 years, 50+ 50-64 years, 65 +, 65--84 years, and 85 + years).

Where data are continuous variables, means and standard deviations will be presented; where these data have a highly skewed distribution, medians, 25th and 75th percentiles will be presented. Where data are categorical variables, the number and percentage of participants within each category will be presented. The percentage of missing values will be reported for each variable (continuous or categorical).

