#### 7.2 Univariate analysis

Univariate analysis will be used to assess outcomes and risk factors; continuous variables will be compared between cases and controls by t-test; categorical variables will be compared between cases and controls by chi-squared (fishers exact where numbers are below 5). Risk ratios (Odds ratio if it is case control study) will be calculated for CDI cases with identified variables of interest. Univariate analysis will be used to assess consistency between countries and between different healthcare settings.

The variables to be included in the univariate analysis are shown in the table in appendix 1.

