#### 7.3 Regression analysis (or Multivariate analysis)

To evaluate risk factors considering confounding, unconditional logistic regression analysis will be perform with case/control as dependent variable, and all variables listed in the univariate analysis as independent variables.

To build the logistic regression model, we will apply a stepwise forward selection to identity risk factors. The process of the forward selection will be recorded to rank the risk factor.

The regression analysis will be performed separately for the three age groups (18-49,50-64 and 65+ years). If there is a reasonable sample size analysis will also be performed for the age group <18 years.

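### The SAP promises data on how the three diagnostic types of CDI differ in severity, risks and outcomes, but plans no comparison of one type with another

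*SAP*

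**What the plan says.** SAP section 1 defines three case types: CCNA positive; CCNA negative but Simoa positive; and free-toxin negative with a toxigenic strain. It then states a purpose: "This enriched case/control study will provide data on the difference in severity of CDI and the risks and outcomes for these different" diagnostic types. It adds that such data are scarce, above all for the Simoa assay.

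The analysis sections read as follows.

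- Section 2.5, objective 1: "Determine the outcomes of cases (of each classification) vs controls", then by country and setting. Objective 2 has the same form for risk factors.
- Section 4.2 says the analysis is based on the different diagnostic criteria. The comparisons it names are: "Comparisons will be made between outcomes and risks for different countries and healthcare settings (hospital, community").
- Section 7.1: "Distribution of demographic, concomitant pathogens, medical conditions, medical procedures, and medication used will be tabulated by case and controls". Severity and outcomes are not in that list.
- Section 7.2: "continuous variables will be compared between cases and controls by t-test", with chi-squared or Fisher tests between the same two groups for categorical variables.
- Section 7.3: logistic regression "with case/control as dependent variable", by age group.

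Appendix 1 collects severity in several places: local grade (4.5.1), temperature, creatinine, white cell count and albumin (5.1–5.4), colitis (5.12), ventilation (5.15) and escalation of CDI treatment (section 7).

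**The concern.** The stated purpose concerns differences between types, but every specified comparison has controls, countries or settings as the other side. A type v control result answers whether that type differs from CDI-negative patients. It does not give the size or uncertainty of the difference between, say, Simoa-only and CCNA-positive patients.

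Severity shows the gap most clearly. CDI severity has little meaning in a CDI-negative control, so that part of the promise needs a comparison among cases. The plan routes the severity items into case v control comparisons instead, and items 5.1–5.4 are marked for univariate analysis only.

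At stake is the question that section 1 itself singles out as lacking data. Any statement about differences between types would have to be constructed after the data are seen, with the choice of contrast, covariates and markers still open.

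**Working it through.** **1. Is the contrast specified anywhere else?** Protocol 3.1.7 compares strain types between cases and colonised participants and by detection method. Protocol 3.2.2 compares mortality by case/control, correct/missed diagnosis and setting. Protocol 3.2.7 compares outcomes by setting, country and strain, and 3.3.7 compares odds ratios on the same three axes. None compares clinical severity, risks or outcomes by diagnostic type.

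**2. Can it be recovered from type v control results?** For a crude odds ratio with shared controls, log OR(type 1 v control) − log OR(type 2 v control) = logit p1 − logit p2, because the control term cancels. A reader with class-level counts could therefore derive a crude ratio for a binary exposure. With adjusted models run by class this need not hold, since forward selection may keep different covariates in each. In neither case is an estimate, interval or test planned.

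**3. Numbers available.** SAP Table 1, headed "Selection of case and controls (total possible to be recruited"), adds up: 103 + 71 + 39 = 213; 213 + 512 = 725; 512/213 = 2.40. These are maxima, before CRF return.

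**4. Do the types differ in setting?** Hospital shares are 83/103 = 80.6%, 49/71 = 69.0% and 24/39 = 61.5%; chi-squared 6.20 on 2 df, p = 0.045. Suppose an exposure is 20–40 points more common in hospital than in community patients (assumed) and does not differ by type. The crude gap between types is then the difference in hospital share times 20–40 points:

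- 1 v 2: 0.116 × 20–40 = 2.3–4.6 points
- 1 v 3: 0.190 × 20–40 = 3.8–7.6 points
- 2 v 3: 0.075 × 20–40 = 1.5–3.0 points

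Stratifying by setting widens intervals by √(crude Σn1n2/(n1+n2) ÷ stratified Σ), assuming equal variance in both settings: √(42.03/41.29), √(28.29/27.19) and √(25.17/25.03), or 0.9%, 2.0% and 0.3%.

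**5. Power of a direct contrast.** The SAP gives none, so the five rate pairs in SAP section 3 (stated there for case v control) are borrowed as an assumption. Power = Φ[(|p1 − p2| − 1.96·s0)/s1], with s0 = √[p̄(1 − p̄)(1/n1 + 1/n2)] and s1 = √[p1(1 − p1)/n1 + p2(1 − p2)/n2]; two-sided 5%, no multiplicity adjustment. Example, 26 v 16%, types 1 v 2: s0 = 0.0638, s1 = 0.0613, Φ(−0.41) = 34%. Ranges cover the higher rate lying in either class.

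| Rates (%) | 1 v 2 | 1 v 3 | 2 v 3 |
|---|---|---|---|
| 26 v 16 | 34–37% | 22–29% | 21–25% |
| 41 v 28 | 42–43% | 29–32% | 27–29% |
| 85 v 75 | 35–38% | 23–30% | 22–26% |
| 67 v 45 | 82–83% | 65–67% | 60–61% |
| 65 v 39 | 93% | 80% | 75% |

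Computing the power of the chi-squared test directly agrees to within about a point. Taking both methods together, the first three rows span about 34–44 / 22–33 / 21–29%.

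**6. Precision.** The unadjusted 95% half-width is 1.96·√[p(1 − p)(1/n1 + 1/n2)]. At 20–50% prevalence this is 12–15 (1 v 2), 15–18 (1 v 3) and 16–20 points (2 v 3).

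**7. Multiplicity and sparse events.** Appendix 1 item 5.7 lists 30 yes/no co-morbidities. With one reference class there are two contrasts each: 30 × 2 × 0.05 = 3 expected false positives if no type differs. If 30-day mortality were 5–15% (assumed), type 3 would have about 2–6 deaths (39 × 0.05 to 39 × 0.15).

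**The case against.** The best counter-text is the opening of section 4.2, which bases the analysis on the different diagnostic criteria, together with the reference to each classification in 2.5. These make the types analysis sets. Section 1 promises data, not a test, so the mismatch could be one loose introductory sentence. What stands is that rewording section 1 would be a sufficient remedy. What does not stand is that 4.2 supplies the contrast: it names no comparison of types, and 2.5 fixes controls as the comparator.

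Four stronger readings are tempting and go too far.

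- **Any statement about types would be unadjusted.** This does not follow. If the 7.3 model is run per class, as 2.5 implies, the type v control odds ratios would be adjusted, and patient location is a candidate covariate, though forward selection may drop it.
- **The SAP means to compare significance verdicts across types.** It nowhere proposes that.
- **A case-case analysis is hopelessly underpowered.** That fits the 10–13 point gaps, but not the 22–26 point gaps also in SAP section 3.
- **Section 4.1.2 removes all type 3 cases.** This is not established. Section 4.1.1(1c) admits a patient who "had a free toxin negative stool sample but was positive for a cytotoxigenic strain", while 4.1.2 excludes GDH-positive/toxin-negative samples without naming the toxin assay. Depending on the assay, type 3 cases could be lost, and possibly type 2 cases as well.

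The setting-mix figures describe a crude case-case contrast that nobody has planned. They argue for adjusting such a contrast and are not an error in the current plan. Planned controls come from the same site and setting as their case.

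**Conclusion.** The gap is real: a stated purpose of the SAP has no planned analysis. Type v control results, adjusted or not, give no planned estimate or interval for a difference between types, and severity can be compared meaningfully only among cases. The case-control objectives in 2.5 are not invalidated, and the data needed are already being collected, so this is a correction that should be made but not a fatal flaw.

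The power and precision figures are best cases. They assume that all 213 case CRFs return, that the section 3 rates are relevant to type v type contrasts, and that the tests are unadjusted and two-sided at 5%. Missing CRFs or markers would widen the intervals. The work is therefore mainly estimation.

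**What to change.** **Option A: add an exploratory case-case analysis to SAP 7.2–7.3**, among the (at most) 103, 71 and 39 cases, with CCNA positive as reference.

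- Severity and outcomes: regress each on class. Cover temperature, creatinine, white cell count, albumin, colitis, ventilation, treatment escalation and the outcomes in Appendix 1 section 10. Report local grade descriptively, because it exists only where the site graded CDI.
- Risk factors: multinomial logistic regression of class on one exposure at a time.
- Adjust for age, sex and hospital/community.
- Where events are few, such as deaths, use exact or penalised methods stratified by setting where possible; otherwise label the contrast as crude.
- Report estimates with 95% intervals, label all contrasts exploratory, and state that non-significance is not evidence of similarity.

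**Option B:** if inference between types is not wanted, narrow section 1 to type v control estimates.

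Under either option, reconcile 4.1.1(1c) with 4.1.2 and name the assay that defines toxin negative, since this decides which types and contrasts exist.

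Option A costs SAP wording and one extra set of models on data already collected. Its drawback is the limited power and the wide intervals shown above. Option B costs wording only.
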